11.4 Systematic errors - bias

Any distortions will be prevented by deriving the indices used for the diagnosis of respiratory and sleep disorders from both methods (Polysomnigraph and Soundi) using the same automatic analysis software (RemLogic).

This will then be followed by manual correction by the operator expert in sleep medicine who is blind to: the identity of the subject under examination, the device with which the data are obtained and the outcome of the same parameters obtained with the comparison device.

To document the patient selection bias, all reasons for non-participation in the study will be recorded on a specific form (Screening Log) and considered in the subsequent statistical analysis.

Impairment of the results or interpretation of the results may be caused by malposition or malfunction of the device.

Specifically, a check of all the sensors when the device is started was included in the design phase. In the event of a malfunction of one of them, it is signaled by a flashing red LED. In this case the measurement can be repeated with another device supplied.

In the event of bad positioning, the measurement results may be compromised and the signal may be incomparable with that acquired by the polysomnography machine. In this last case the measurement is unusable for the study and the patient data will not be included in the effectiveness analysis.

How to minimize these biases is further detailed in the dossier for the investigator.

12.Medical device

It is planned to use 2 experimental devices (SOUNDI system, Biocubica) and 1 product

comparison (polysomnograph, Embletta, Natus).

The experimental SOUNDI devices will be supplied by the Promoter and will be identified by a batch number and a serial number.

The Investigator will be responsible for keeping track of the experimental devices from their delivery to the center until they are returned to the Sponsor at the end of the study.

The devices will be stored centrally in a secure location where only authorized personnel can access them and at a temperature between -25°C and +70°C and a relative humidity of less than 93%, as indicated by the manufacturer, until delivery to the patient.

If a device is lost or damaged, the Investigator will notify it immediately to the Promoter.

The polysomnograph (Embletta, Natus) is already present at the center as it is used for clinical practice.

13. Ethical and regulatory aspects

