The current prototype of the Soundi device was developed on the basis of a technology patented by Biocubica (Italian patent no. 102016000052588 "Physiological monitoring device" and European patent EP3.248.541 "Physiological monitoring device") (1) and is equipped with the ability to listen, through a particular bell shape, to all the sound evidence nothing from our body and generated at different frequencies by different organs and/or muscles and tissues, and transduce them, through a series of sensors and with appropriate algorithms, into different vital signals.

Specifically, the parameters Soundi detects are:

- Temperature
- Heart rate
- ECG
- Oxygen saturation
- Respiratory rate
- Flow
- Snoring
- Nocturnal posture
- Numeropassi.

Soundi is also able to record environmental parameters in which the individual lives, in particular it detects temperature, relative humidity, pressure, CO2 equivalent, Volatile Organic Compounds (VOC) produced by human breathing (for example CO) and by the environment (for example formaldehyde).

Soundi is a small (diameter of 60 mm and height of 12 mm), lightweight, which is applied with a double-adhesive medical patch on the left hemithorax and can record the parameters over 24 hours for up to 15 consecutive days. Equipped with a rechargeable battery, it is capable of providing continuous measurement of the main physiological parameters.

Soundi is made up of the following components (Figure 1):

1. multi-sensor measuring unit (Figure 2)
2. ignition key

3. a double-adhesive medical plaster.

Figure 1. SOUNDI:1.Measurement unit;2.Ignition key;3.Double-sided medical tape.

[figure not shown]

Figure2. Image of the SOUNDI multisensor measurement unit

Soundi is supplied with the following accessories:

- 1-channel ECG cable
- USB cable to allow charging of the rechargeable battery and connection to the PC
- power supply
- software pcSOUNDIDOC.

The device will be used for full cardiorespiratory monitoring.

Being a wearable device also intended for non-hospitalized patients, SOUNDI is also intended to be used in a home environment.

The SOUNDI device records in internal memory the physiological data of the monitored person. The data is then downloaded, via USB cable, to the PC to be converted into a file with standard edf, the same format as the file returned by the standard polysomnography device.

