3.3 Risks and benefits

The main risks associated with the use of the SOUNDI device by the subjects included in the clinical investigation are:

- Discomfort associated with positioning/removing the measurement unit using double-sided adhesive medical
- Allergic reaction to double-sided adhesive components

These risks will be minimized by the training of the personnel who will place and remove the device from the subject and by the exclusion from the study of subjects with a known allergy to the components of the double-sided adhesive.

The intrinsic risks most related to the design of the device (explosion/fire of the battery, electrocution linked to electrical leakage, emission of electromagnetic radiation, etc.) were evaluated and minimized in the design phase and verified through laboratory tests (electrical safety and electromagnetic compatibility).

The simultaneous collection of vital signs may allow for an early diagnosis of OSA in subjects suspected of having a sleep disorder.

Furthermore, the clinical validation of the SOUND I device on patients will allow the marketing of a small, handy and inexpensive device for the continuous monitoring of vital parameters, capable of collecting useful information for the early diagnosis or follow-up of breathing disorders in sleep.

4. Study design

This is a pre-marketing, single-center, prospective clinical investigation to compare the effectiveness and safety of the SOUNDI medical device compared to polysomnography in detecting parameters for the diagnosis of OSA in subjects suspected of having a sleep disorder.

The study expects to enroll 50 patients.

All patients belong to the Sleep Medicine Center of the Italian Auxological Institute IRCCS-San Luca Hospital in Milan.

After signing the informed consent, the Sound device will be placed in all eligible subjects and at the same time as a traditional polysomnography device the activation of the devices for the acquisition of the parameters will be programmed so that it begins when the subject lies down.

The signals will be acquired for approximately 8 hours during a single night with both systems simultaneously and will then be calculated, via automatic analysis software, with subsequent manual correction by a doctor expert in sleep medicine, the indices used, according to international guidelines, for the diagnosis of breathing and sleep disorders.

No further follow-up is planned for subjects.

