6.3 Exclusion criteria

- Women during pregnancy
- Insufficient cooperation/degree of collaboration in following the procedures required by the study
- Participation in another clinical study.
- Allergy to one of the materials in the device
- Pacemaker users.

7. Study procedures

All subjects enrolled in the study will undergo polysomnography (monitoring

nocturnal cardiorespiratory for the diagnosis of apnea in sleep) with traditional polysomnography (Embletta, Natus) according to normal clinical practice and at the same time as data acquisition with the Soundi system.

On the afternoon before the night of the evaluation, at the Sleep Medicine Service clinic, each object will be placed

- a traditional polysomnigraph, as prescribed
- the Soundi experimental device.

The patient will be instructed by the Investigator on the correct management of the devices.

During the visit, the following anthropometric data will be collected: age, Body Mass Index (BMI), neck circumference and abdomen.

Furthermore, the Experimenter will program the devices to begin recording the parameters at the moment the subject expects to recharge and continue for at least 8 consecutive hours.

During the night, at the patient's home, the following parameters will be acquired with two systems: oro-nasal flow, thoracic and abdominal respirations, snoring, ECG, arterial oxygen saturation (SaO₂), body position.

The following morning the subject will return to the clinics to return the two systems which will be detached by the medical staff. There, the subject will be asked to fill out a simple satisfaction questionnaire prepared for the study.

The signals acquired with both systems simultaneously will be processed by the software RemLogic, via automatic analysis software, with subsequent manual correction by a doctor expert in sleep medicine, the following indices used, according to international guidelines, for the diagnosis of respiratory and sleep disorders:

- Apnea Hypopnea Index (AHI) total and supine
- AHI central
- AHI obstructive
- Oxygen Desaturation Index (ODI)
- Average arterial oxygen saturation (SaO₂).
- Minimum SaO₂
- Time with SaO₂ < 90%
- Average heart rate
- Minimum heart rate
- Percentages of time spent in different body positions.

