8.1 Interruption and withdrawal of subjects from the clinical investigation

Each patient is free to withdraw from the study at any time or his participation may be interrupted by decision of the trial for safety, behavioral or reasons administrative.

Reasons for discontinuing a patient's participation in the study may include:

- withdrawal of consent by the patient
- the change in the patient's clinical-functional conditions that do not allow participation
- lack of adherence to the procedures required by the study protocol on the part of the patient
- an adverse event (related or unrelated to the study device) which, in the opinion of the Principal Investigator, does not allow the continuation of the study itself.

If the study is interrupted for any of the reasons listed above, the measurements taken will not be considered in the statistical analysis.

The reasons for stopping the study will be recorded in CRF.

Unless particular problems are reported to the patient (adverse events or effects related to the use of the device in the study) which will be followed by specific assessments, a follow-up will not be necessary.

Patients excluded from the study and who cannot obtain the data required by the study protocol will be replaced to reach the required number.

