15.3 Document storage

The Investigator will have to keep the documentation relating to this clinical investigation for at least 10 years from the conclusion or for a longer period, if required by the applicable legislation.

The documentation of the clinical investigation must be kept in a safe place which, if necessary, allows for timely recovery.

If the Investigator wishes to transfer the clinical investigation documents to another location, he/she must inform the Sponsor in advance.

16. Insurance

The insurance coverage of the risks relating to the study is guaranteed by an insurance policy stipulated ad hoc by the Promoter pursuant to the Ministerial Decree of 14 July 2009. The insurance coverage will be covered by the Promoter.

17. Steering Committee

This study will have a data monitoring steering committee which will include representatives of the Promoter and the Principal Investigator. All study endpoints, objectives and safety data will be reviewed regularly by the steering committee which will meet periodically in order to carry out a timely analysis of the tests progressively carried out. The steering committee will have the possibility to decide to suspend the investigation in case of security problems and may

recommend changes to the investigation, including discontinuation, if there is a change in the risk/benefit ratio for participating subjects.

18.Bibliography

[1]PhysiologicalMonitoringDevice

<https://worldwide.espacenet.com/patent/search/family/056940255/publication/EP3248541B1?q=pn%3DEP3248541B1>

[2]Marzorati,D.,Bovio,D.,Salito,C.,Mainardi,L.,&Cerveri,P.

(2020).ChestwearableapparatusforcufflesscontinuousbloodpressuremeasurementsbasedonPPGandPCGsignals. *IEEEAccess*, 8, 55424-55433.

[3]Marzorati,D.,Dorizza,A.,Bovio,D.,Salito,C.,Mainardi,L., &Cerveri,P.(2022).HybridConvolutionalNetworksforEnd-to-EndEventDetectioninConcurrentPPGandPCGSignalsAffectedbyMotionArtifacts.

IEEE Transactions on Bio-medical Engineering.

[4]Rossi,M.,Alessandrelli,G.,Dombrovski,A.,Bovio,D.,Salito,C.,Mainardi,L.,&Cerveri,P.(2022).IdentificationofCharacteristicPointsinMultivariatePhysiologicalSignalsbySensorFusionandMulti-TaskDeepNetworks. *Sensors*,22(7),2684.

[5]RossiM.,SalaD.,BovioD.,SalitoC.,AlessandrelliG.,LombardC.,MainardiL.,CerveriP.(2022) SLEEP-SEE-THROUGH:explainabledeeplearningforsleepeventdetectionandquantificationfromwearablesomnography. *SubmittedtoIEEEJournalofBiomedicalandHealthInformatics*.

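### Section 11.4 describes the exclusion of badly positioned SOUNDI recordings partly by comparison with the polysomnograph, with no independent test of malposition and no stated blinding for the decision

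*Protocol*

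**What the plan says.** Section 11.4 discusses malposition and malfunction as sources of bias. A sensor malfunction at start-up is signalled by a red LED, and the measurement can be repeated with another device. For bad positioning it says that results may be compromised and that "the signal may be incomparable with that acquired by the polysomnography machine. In this last case the measurement is unusable for the study"; the patient's data then leave the effectiveness analysis.

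The same section describes blinding for one step: "This will then be followed by manual correction by the operator expert in sleep medicine who is blind to" the subject's identity, the device and the result from the other device. It closes with a pointer to another document: "How to minimize these biases is further detailed in the dossier for the investigator".

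Other relevant text in the protocol:
- Section 7.1 counts a test as valid if no artifact invalidates the signals over at least 4 hours.
- Section 11.3 excludes measurements under 4 hours caused by malfunction or malposition. The list is broken in the text at hand.
- Section 8.1: "Patients excluded from the study and who cannot obtain the data required by the study protocol will be replaced to reach the required number".
- Section 3.3 relies on "the training of the personnel who will place and remove the device from the subject". Section 3 gives the site: the device is "applied with a double-adhesive medical patch on the left hemithorax". Under section 7 the patient comes back next morning to "return the two systems which will be detached by the medical staff".
- Sections 9.1 and 11.1 make agreement with the polysomnograph, by CCC and Bland-Altman plot, the primary question.

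**The concern.** An agreement study needs its exclusions decided without sight of the agreement. Here the sentence that removes a recording refers to the comparator, and malposition has no criterion of its own to fall back on. Someone who sees a SOUNDI trace that does not match the polysomnograph could reasonably infer that the device was badly placed.

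If the device really was badly placed, dropping the recording does not bias agreement under correct use. If it was correctly placed and simply disagreed, dropping and replacing it raises the CCC and narrows the limits of agreement. As worded, the protocol offers no way to tell the two cases apart, and a final count of 50 would not show the loss. Device defects, which under section 10.2 include errors in use, are reported with safety under 11.2, so some losses would be visible there.

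**Working it through.** **1. Does anything in the protocol test malposition without the comparator?**

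- Section 7.1 tests artifacts and duration, not position.
- Section 11.3 names malposition but does not define it. This is so whether the broken list makes malposition a cause of short recordings or a separate item.
- The LED in 11.4 tests sensor function at start-up, not position.
- Trained staff fit and remove the device at a stated site, but no position check at removal is specified.
- The stated blinding covers manual correction. No assessor, timing or blinding is given for the usability decision.

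The words *in this last case* in 11.4 have two readings: malposition in general, or only malposition with an incomparable signal. Both need a judgement of malposition, and neither comes with a comparator-free criterion.

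**2. The plan's own sample size**

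Inputs from the sample-size paragraph under section 11.2: CCC 0.60 under H0, 0.81 under H1, 5% significance (read as one-sided), 90% power, 50 analysable patients.

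Fisher z: atanh(0.81) − atanh(0.60) = 1.127 − 0.693 = 0.434.
n = ((1.645 + 1.282)/0.434)² + 3 = 48.5, so 49.
Power at 50 = Φ(0.434·√47 − 1.645) = 90.8%.

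The plan's figure reproduces and the sample size is not in question. A two-sided 5% test would need 59, which supports the one-sided reading.

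**3. What wrongly dropped recordings could do (illustration, not an estimate)**

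The protocol gives no malposition rate, so the number dropped, k, and the selection mechanism are assumptions.
- Data: bivariate normal pairs with equal means and variances, and 50 + k correctly placed pairs.
- Selection: k pairs are removed (at random; at random within the half or quarter with the largest absolute differences; or exactly the k largest), leaving 50.
- Test: one-sided 5% Fisher-z test of CCC > 0.60 with the normal-theory variance, 20,000 runs per cell.
- Calibration with no drops: rejection is 4.5% at true CCC 0.60 and 91% at 0.81, in line with the planned 90%.

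False success at true CCC 0.60:

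| Wrong drops | Unrelated to agreement | More discordant half | Most discordant quarter | Exactly the most discordant (upper bound) |
|---|---|---|---|---|
| 1 | 4.6% | 5.2% | 6.1% | 10.2% |
| 2 | 4.6% | 6.0% | 8.1% | 16.8% |
| 3 | 4.2% | 6.7% | 10.1% | 24.3% |
| 5 | 4.6% | 8.5% | 16.7% | 41.0% |

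Repeat runs agreed to within about one percentage point. With two drops the mean CCC is 0.59, 0.60, 0.61 and 0.65 across the columns. The half-width of the limits of agreement is 1.74 SD with no drops and 1.72, 1.68 and 1.57 SD in the last three columns, so it narrows by at most about 10% (1 − 1.57/1.74).

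**The case against.** **Malposition is always the premise.** A reader might infer that 11.4 tells staff to drop discordant recordings. It does not: no text makes disagreement itself a ground, and *incomparable* may mean no more than unreadable. The document is visibly a translation, so little weight should rest on single words. This stands. The point is only that poor agreement could serve as evidence of malposition when nothing else defines it.

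**Section 7.1 already protects a clean recording.** It calls such a recording valid, and 11.3 does not mention the comparator. This stands in part. It makes 11.4 a text in tension with 7.1, but 11.4 carries no duration or artifact limit, and nothing says which section prevails.

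**Criteria, assessor and blinding are details for the SAP or the investigator's dossier.** Neither is shown, and either may help. But the protocol itself fixes this exclusion, in the section meant to prevent bias, and its wording would still refer to the comparator.

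**The simulation models something else.** It selects on the difference in one index, while 11.4 speaks of the signal. Section 7 lists about ten indices, and a patient discordant on one need not be so on the others. *False success* borrows the hypothesis of the sample-size paragraph, whereas 11.1 describes CCC bands and a plot. All this stands, which is why the figures are an illustration and the last column an upper bound.

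**The steering committee.** A reader might infer from section 17, where sponsor representatives and the principal investigator review endpoints during the study, that exclusions would be made with the results in view. The protocol does not say that the committee decides exclusions, so this carries no weight here.

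**Conclusion.** The point holds as a weakness of wording and safeguard, not as evidence that discordant data will be removed. Section 11.4 describes an exclusion partly in terms of the primary comparator, without a comparator-free test of malposition, without stated blinding for the decision, and with replacement available.

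The size is unknown. Under the assumed mechanisms, one or two wrongly dropped recordings matter little: false success of about 5 to 8% against 4.5% if they come from the more discordant half or quarter. The large figures, up to 41% with five drops, require exactly the most discordant recordings to be removed, and nothing in the protocol suggests that. Exclusions unrelated to agreement, or of truly malpositioned recordings, do not bias agreement under correct use. The matter should be fixed because the remedy is cheap; confidence is medium because of the ambiguous text and the unseen dossier.

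**What to change.** In section 11.4:
- Delete comparability with the polysomnograph as a ground for exclusion and refer to the validity rules of 7.1 and 11.3.
- Have usability judged on each recording alone, by a named role blind to the paired recording and its indices, and fixed before pairing.
- State that a recording valid under 7.1 stays in the analysis even if it disagrees.

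Staff may note device position at morning removal as supporting information. It does not show position during the night, so on its own it should not exclude a recording that is valid under 7.1.

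As support, with detail that can sit in the SAP, report the number of unusable recordings per device with reasons, and a sensitivity CCC on all pairs with computable indices.

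The cost is a wording change, one optional item at removal and two outputs. The primary CCC may be slightly lower because clean but discordant recordings stay in. The sensitivity CCC can be clearly lower and should only support. For example, with true CCC 0.81 in 50 pairs, adding 5 malpositioned pairs with an assumed CCC of 0.6, 0.3 or 0 moves the mean estimate from 0.80 to 0.78, 0.76 or 0.73.

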13.1 Ethical management of the clinical investigation

The clinical investigation will be conducted in full compliance with the provisions of international legislation and its national transposition regarding clinical trials and the principles of the Helsinki Declaration with the aim of ensuring maximum protection of the subjects involved.

and in accordance with the Medical Devices Regulation (EU) 2017/745 and ISO14155:2020.

The Principal Investigator is responsible for the correct conduct of the clinical investigation in accordance with the provisions of this protocol, any future amendments, the other procedures envisaged by the Sponsor and the Good Clinic Practice (GCP).

13.2 Regulatory aspects

The clinical investigation is subject to review and approval by the Competent Authority and the Ethics Committee.

The written approval of the relevant Ethics Committee must be obtained before the start of any study-related procedure and must be documented through official communication to the Investigator.

If during the course of the trial, substantial changes to the study protocol become necessary, the Sponsor will submit an appropriate request for an amendment to the Ethics Committee and the Competent Authority. The authorization of the Ethics Committee and/or the Competent Authority will be necessary before their application.

